7.6. Participant Timeline – Full Study

7.6.1. Time 0: Invitation to inquire about enrolling in the study

Each CF center will contact eligible patients by whichever means approved by their IRB (email, phone), inviting all current female patients, ages 18-45 years who are participants in the CFFPR to participate in the study. Eligible patients will also be approached at their clinic visits. For CF centers who want the UW research team to contact eligible patients, they will send a list of eligible patients, email, and CFFPR member ID to the study team.

7.6.2. Time 1 (V0): Enrollment procedure

- 1. Each CF center will identify all female patients with CF, ages 18-45 years who have a CFFPR patient registry ID number.
- 2. Each CF center will send an email with information about the study to all female patients identified in step #1. If they prefer the UW research team to contact eligible patients, they will send a list of eligible patients, email, and

CFFPR member ID to the UW, and the UW research team will send an email with information about the study to eligible patients.

- 3. Each CF center also approach female patient identified in Step #1 when they are seen in the clinic with written information about the study.
- 4. Interested potential participants will receive the link the online survey to complete the eligibility questions and consent form via email. This link will come from either the UW research team or CF center staff, depending on CF center preference.
- 5. The potential participant will answer screening questions via the online portal to ensure eligibility.
- 6. If the participant qualifies for the study, they will be consented to participate via the online portal.
- 7. Once consented, the participant will move forward to the online survey itself. To help reduce recall bias, pictures of most birth control pill packages as well as other birth control methods will be accessible as the participant completes the survey.
- 8. In order to maximize response rates, participants will be sent automatic reminders to complete their survey using REDCap reminder features.
- 9. Compensation to the participant will be provided by the UW research team once survey is complete and the UW research team has verified that they are in the CFFPR (about 2 weeks after completion of the survey).
- 10. The UW research team will receive CFFPR data, which includes whether patients have a diagnosis of osteopenia or osteoporosis. Among those with a positive diagnosis, the research team will randomly select 10 participants from each CF center, in order to compare CFFPR data to DXA scan results from CF centers.
- 11. Providing DXA scan results: Once the 100 participants have been confirmed as having completed the enrollment, consent form, and survey by the UW research team, and CFFPR data indicates a diagnosis of osteopenia or osteoporosis, the UW research team will provide the appropriate CF center with a case report form (CRF), labelled with the participant's survey study ID number only. The CF Center research staff will have access to a password protected database in REDCap that links the survey ID number with participant name and date of birth (for patients at their CF center only). The name and date of birth will be used for the CF Center to complete the case report form using the participant's electronic medical record (EMR) data.
- 12. The CF center research staff will complete the CRF that asks for DXA scan scores (from 2013 to 2018).
 - a. CF research staff will report T-scores from 3 anatomical sites: femoral neck, lumbar spine and total hip.
 - b. Verification with CFFPR: We will take the lowest BMD T-score reported for either the femoral neck, lumbar spine, or total hip when categorizing a participant as osteoporotic, osteopenia, or normal for a given DXA test within a given year and compare to the diagnosis of record in the CFFPR. Scores provided at other anatomical sites (forearm, heel, etc.) will not be considered.

Table 6: Outline of responsibilities of clinic

Clinic responsibilities			
	Pre-enroll	Enrollment	Post-enroll
Month	0	1-12 months	13-15 months
 Send invitations to participate in study, followed by phone call, and approach women in clinic to participate 	х		
 CF center research staff to give patient's unique CFFPR ID number, name, DOB, and contact information to UW research team 		х	
CF clinic research staff to complete case report form:			Х

0	DXA scan results: dates and results as far back as 2013. Results		
	will include T-scores from 3 sites: femoral neck, lumbar spine and		
	total hip and year that DXA scan was performed.		

Table 7: Outline of responsibilities of Study Participant (Patient)

Participant responsibilities		
	Pre-enroll	Enrollment
Month	0	1-15 months
• Enroll in study		Х
• Be willing to be contacted by UW research team staff member		Х
 Complete smoking and blood clot questions 		Х
 Complete CFTR modulator questions 		Х
 Complete surgical history questions 		Х
 Complete contraception questions 		Х
Complete menstrual questions		Х
 Complete pregnancy history questions 		Х

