- (4) Does hormonal contraceptive use affect nutritional status for women with low body mass index?

- (5) What is the percent agreement between CF Clinic DXA scan T-scores and CFFPR data about osteoporosis, osteopenia and bone fracture?
- (6) Are women who use CFTR modulators and more likely to become pregnant unintentionally while taking hormonal contraception (compared to women on non-hormonal contraception)?
- (7) Does use of hormonal contraception result in a higher proportion of patients with mucoid vs. non-mucoid *Pseudomonas aeruginosa* compared to non-hormonal contraceptive users?

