3.0. Hypothesis

- Estrogen-containing methods, but not progestin-only methods, reduce the annual rate of pulmonary exacerbations, the microorganisms associated with a more rapid decline in lung function, and improve ppFEV1 (or absolute FEV1) of women with CF when compared to women with CF who use non-hormonal contraception (control group).
- Estrogen-containing oral methods of birth control are associated with higher incidence of gallbladder disease (defined as gallstones, requiring surgery), increased liver function enzyme values, and/or increased incidence of thromboembolism among women with CF.
- Both estrogen-containing and progestin-only hormonal methods improve BMI among women with CF, which is linked to nutritional status.
- The strength of agreement between DXA scan T-scores and CFFPR data about osteoporosis, osteopenia and bone fracture will be "substantial."
- The effectiveness of oral birth control is reduced compared to other methods of hormonal birth control in the presence of CFTR modulator use.
- Hormonal birth control use results in a greater proportion of patients with mucoid *Pseudomonas aeruginosa*, in patients who are *P. aeruginosa* positive, compared to non-hormonal contraceptive users.

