5.0. Trial Design

This is a non-randomized, non-interventional, observational cohort design among reproductive-aged women (ages 18-45 years) with CF. This protocol describes a pilot phase, as well as a larger retrospective approach.

We intend to ask about 625 female participants to provide information about their types of past contraceptive use from 2008 through the most recent data available from CFFPR (2018 or 2019). Before initiating our trial among up to 625 respondents, we intend to pre-test the survey questions on our self-respondent questionnaire among as many as 50 women with and without CF through CFF Community Voice, the Cystic Fibrosis Research, Inc. (CFRI), and the Cystic Fibrosis Reproductive and Sexual Health Collaborative (CFReSHC). Pre-testing our survey questions will help ensure contraceptive, pregnancy, and other reproductive health data from respondents for the larger phase of this study are as complete and accurate as possible.

Once the survey has been piloted and revised accordingly, we will collect past contraceptive, pregnancy and other reproductive health data from up to 625 women at 10 different CF centers. We may over-sample by 25 participants because it is possible that some participants from UW, UTSW and National Jewish may have participated in our earlier published study related to contraceptive use and CFFPR (4). Recruiting through the CF centers will help ensure that women with a confirmed diagnosis of CF respond to the finalized survey. We will link respondent self-reported contraceptive and reproductive health data with CFFPR clinical data. We will ask for EMR data from the 10 different CF centers to validate DXA scan results with findings regarding osteoporosis, osteopenia, and bone fracture in the CFFPR. We plan to randomly select about 10 consented subjects from each of the centers for the EMR DXA scan chart review. Because of our need to link questionnaires and clinical case report forms correctly to the same women with CF in the CFFPR clinical data, we need to request identifiable information, including the CFFPR member ID number.

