7.3. Interventions

We will provide an online questionnaire to give to female participants in order to obtain exposure data (past contraceptive use). We will have participants complete the survey on their own, either in clinic or at home. The survey will include pictures, brand names, and descriptions to help respondents remember birth control method used retrospectively.

We will ask each CF center to provide DXA scan results for 10 participants (selected at random) from their respective EMRs in order to validate osteoporosis, osteopenia and bone fracture information in the CFFPR.

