We will assess the strength of agreement between CFFPR reported data on osteoporosis, osteopenia and bone fracture compared to gold standard clinic DXA scan T-scores. We calculate the percent overall level of agreement between the CFFPR and clinical BMD scores using Cohen's kappa statistic calculation. Level of absolute agreement represents the proportion of participants for whom the CFFPR and clinic DXA scan T-score were correct. We will also report on proportion of scores entered within the year or year after DXA scan was completed, versus scores entered 3-5 years after DXA scan completed.

Missing Data

We will plan to impute missing data as our primary analysis. Should we discover large amounts of missing data, we will perform a sensitivity analysis excluding women with missing data to explore how findings differ from those without missing data.

Computer Facilities

Appropriate computer facilities are readily available for data analysis. REDCap will be used for entry and preparation of data for statistical analysis. Statistical analysis will be performed using STATA 12.

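### The DXA chart review samples only women already coded low in the registry, so the planned kappa cannot measure registry-wide agreement

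*Combined protocol and SAP*

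**What the plan says.** Three sections describe how charts are chosen for the DXA validation.

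- Section 5.0: "We plan to randomly select about 10 consented subjects from each of the centers for the EMR DXA scan chart review".
- Section 7.3: "We will ask each CF center to provide DXA scan results for 10 participants (selected at random) from their respective EMRs".
- Section 7.6.2, step 10: "Among those with a positive diagnosis, the research team will randomly select 10 participants from each CF center". Step 11 repeats the restriction: the case report form goes out once "CFFPR data indicates a diagnosis of osteopenia or osteoporosis".

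The first two set no diagnosis condition; the third does. Step 12b nevertheless keeps three categories, "when categorizing a participant as osteoporotic, osteopenia, or normal for a given DXA test within a given year".

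The stated target is broad. Research question 5 in 2.0 asks: "What is the percent agreement between CF Clinic DXA scan T-scores and CFFPR data about osteoporosis, osteopenia and bone fracture". Section 3.0 predicts: "The strength of agreement between DXA scan T-scores and CFFPR data about osteoporosis, osteopenia and bone fracture will be" substantial. Section 9.3 says: "We calculate the percent overall level of agreement between the CFFPR and clinical BMD scores", using Cohen's kappa, and has no weighting or other correction for a restricted sample.

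**The concern.** Under steps 10-11, selection depends on one of the two ratings being compared. A woman whose registry record never shows a low diagnosis has zero probability of entering. Two kinds of women are therefore lost: those correctly recorded as normal, and those with a low T-score whom the registry missed. Without them, the registry's sensitivity, specificity and overall kappa cannot be estimated. Weighting cannot repair this, because there is nothing to weight in a stratum sampled with probability zero.

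The missed cases matter here because Table 5 and 9.3 list osteoporosis and fragility fracture as study outcomes. A validation that cannot see under-recording could endorse registry bone data that miss many affected women.

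**Working it through.** **Count.** 10 centers × 10 charts = 100, which reproduces the figure in step 11. The plan states no precision for kappa.

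**Low versus normal.** With one registry diagnosis per woman, every sampled woman is registry-low. Percent agreement is then the positive predictive value (PPV). Observed and chance agreement are both equal to the PPV, so a two-level kappa is 0 (undefined if every DXA is low). The plan does not announce this two-level statistic; it shows what the sample lacks.

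**Three levels.** Kappa = (Po − Pe)/(1 − Pe). The rates below are assumptions. Tables are per 100 women; rows are registry normal / osteopenia / osteoporosis, and columns are DXA in the same order. Grade swaps apply to detected low women, and false positives are coded osteopenia.

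- *Scenario A*: DXA 60/30/10%, 20% of low missed, 5% false positives, 10% swaps. Table: [57, 6, 2; 3, 21.6, 0.8; 0, 2.4, 7.2].
- *Scenario B*: DXA 40/45/15%, 50% of low missed, 2% false positives, 5% swaps. Table: [39.2, 22.5, 7.5; 0.8, 21.375, 0.375; 0, 1.125, 7.125].

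| | Po | Pe | Kappa | PPV |
|---|---|---|---|---|
| A, all women | 0.858 | 0.476 | 0.729 | |
| A, registry-positive only | 0.823 | 0.560 | 0.597 | 0.914 |
| B, all women | 0.677 | 0.391 | 0.470 | |
| B, registry-positive only | 0.925 | 0.600 | 0.813 | 0.974 |

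Example for A, registry-positive only: Po = (21.6 + 7.2)/35 = 0.823. Pe = (25.4 × 24 + 9.6 × 8)/35² = 0.560. Kappa = (0.823 − 0.560)/(1 − 0.560), which is 0.597 before rounding. Coding half of the false positives as osteoporosis changes the restricted kappas only to 0.61 (A) and 0.82 (B).

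**One observed table, many possible registries.** Suppose the 100 registry-positive charts give, with DXA in the same column order, 10/62/5 for registry osteopenia and 1/4/18 for registry osteoporosis.

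- Po = (62 + 18)/100 = 0.80
- Pe = 0.77 × 0.66 + 0.23 × 0.23 = 0.561
- Kappa = 0.54

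Now vary only what the sample cannot see: the registry-low share from 30% to 50%, and missed low density among registry-normal women from 5% to 40% (split 85/15 between the two grades). The registry-wide three-level kappa then runs from 0.41 to 0.79, with identical observed data.

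**Unit of analysis.** Step 12b compares each test within a year, whereas 9.3 counts participants. With test-years as the unit, some registry-normal years may enter, but only from women coded low in another year, so the selection remains. This case is not quantified here.

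**The case against.** Sections 5.0 and 7.3 can be read as short overviews that steps 10-11 fill in, and confirming positive records is a legitimate, narrower aim. The question and hypothesis do name osteoporosis, osteopenia and fracture rather than normal results. But 9.3 plans an overall level of agreement with kappa, and step 12b keeps a normal category. Neither fits a positives-only aim, so the target must at least be stated.

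Scenario B is favorable to inflation. Holding 50% missed and varying low density from 20% to 60%, false positives from 2% to 20% and swaps from 5% to 10% gives a positives-only kappa between 0.11 and 0.81, with B at the top. That limits what can be said about size and direction. It does not restore the missing stratum.

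Two points on the remedy stand. A plain random draw of 100 women with a recorded DXA does about as well as a weighted 50/30/20 stratified draw: the SD of kappa is 0.065 (A) and 0.069 (B), against 0.063 and 0.062. Stratification is therefore optional. The plan must also name the registry field being validated, because the Appendix requests both a DXA result (part IV) and osteopenia/osteoporosis as complications (part VII).

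**Conclusion.** The concern holds. The sampling frames contradict each other, and the one in steps 10-11 cannot support the overall agreement claim in 3.0 and 9.3. That conclusion needs no assumed rates: women never coded low cannot be selected. What remains estimable is the PPV of a low registry code, and osteopenia-versus-osteoporosis agreement among registry-positive women.

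The size does rest on assumptions. Kappa is understated by about 0.13 in A (0.73 to 0.60) and overstated by about 0.34 in B (0.47 to 0.81), taking one registry diagnosis per woman. This should be fixed before charts are drawn. It concerns one secondary objective.

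**What to change.** 1. Reconcile 5.0, 7.3 and 7.6.2 on a single sampling frame. To keep the overall agreement claim, draw the same roughly 100 charts from consented women with any DXA result in the registry for 2013-2018: normal, osteopenia or osteoporosis. A simple random draw is enough. If stratified by registry category (for example 50/30/20), record the sampling fractions and use inverse-probability weights.
2. Set any strata across centers. The smallest center lists 51 women, about 26 at 50% enrollment, and may not fill each stratum.
3. Report kappa, percent agreement, sensitivity and specificity with confidence intervals. Fix the unit (woman or test-year) and name the registry field. State that results apply only to women with a registry-recorded DXA. Scans never entered stay unseen, and women with a complication diagnosis but no recorded result fall outside the frame.
4. If the positives-only draw is kept, report agreement among registry-positive women (PPV) and drop the overall kappa claim from 3.0 and 9.3.
5. Two separate corrections: the case report form collects only DXA scores, so remove bone fracture from the DXA agreement claim; and 4.2 says one center where other sections say ten.

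The cost is protocol wording and a different draw of the same number of charts. The normal result is already requested (Appendix, part IV), and consent to release DXA results is an inclusion criterion for everyone (Table 4). In simulation (8,000 draws of 100 charts, center clustering ignored), the 50/30/20 design gives 95% ranges for kappa of 0.60-0.85 in A and 0.36-0.60 in B. The positives-only draw gives 0.43-0.75 and 0.67-0.93, centered on the wrong values.

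The price is precision on PPV, because half as many registry-positive charts are read: in A its range is 0.83-0.98 instead of 0.86-0.96. Sensitivity stays imprecise (0.69-0.93 in A).

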The definitions for normal bone, osteopenia, and osteoporosis are based on bone mineral density (BMD) scores. BMD is measured by dual energy X-ray absorptiometry (DXA), which provides both T-scores and Z-scores. These scores are used to define whether a person is categorized as having osteoporosis, osteopenia, or normal bone. According to the World Health Organization (WHO), the T-score is the number of standard deviations (SD) above (+) or below (-) the mean BMD in a young, normal, sex-matched population and is preferred for postmenopausal women. The Z-score is the number of standard deviations (SD) above (+) or below (-) the mean bone density in a normal, sex- and age-matched population and is preferred in females prior to menopause (7). In contrast to WHO criteria, the CFF uses Z-scores for children less than 18 years, considers T- and Z-scores as nearly equivalent for persons between ages 18-30 years, and uses T-score findings for persons with CF ages 30 years and older (8).

Our project is specifically designed to collect more information on these critically important issues by expanding our pilot contraceptive CFFPR study and further assess the safety and efficacy of contraception among patients with CF. With pilot funding from the Society of Family Planning, Drs. [name], [name], and [name] collaborated with two other CF centers to assess feasibility, data completeness, and data accuracy of a pilot contraceptive registry. Having successfully linked women with CF's self-reported information on current and prior contraceptive use with clinical data information obtained from the CFFPR, we are now ready to expand our work to include seven additional CF Centers for a total of ten centers (see Table 2).

The research questions we aim to answer for women with CF, aged 18-45 years in this retrospective study include:

- (1) Are estrogen-containing or progestin-only hormonal contraceptives associated with improved objective pulmonary symptoms compared to women with CF who use non-hormonal methods (control)?
- (2) Are estrogen-containing or progestin-only hormonal contraceptives associated with increased incidence of CFrelated liver disease (as noted with increasing trend of liver enzyme tests), gallbladder disease or thromboembolism?
- (3) Are estrogen-containing or progestin-only hormonal contraceptives associated with increased serum glucose trends (as measured by oral glucose tolerance testing) compared to women using non-hormonal methods?

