9.1.2. Clinic Case Report Forms (CRF)

We are requesting CRFs from each of the 10 CF centers in order to verify DXA scan findings with bone data reported in the CFFPR.

Table 9: Information sought on CRF

EMR Data Request

• DXA scan results: dates and results as far back as 2013. Results will include T-scores and Z-scores from 3 sites: femoral neck, lumbar spine, and total hip and date that DXA scan was performed.

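### DXA scans taken before age 18 are classified by T-score, although the protocol says the CFF uses Z-scores at that age, so some scans may be misclassified or unclassifiable

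*Combined protocol and SAP*

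**What the plan says.** Section 7.6.2, step 12b, sets the study category for each scan: "We will take the lowest BMD T-score reported for either the femoral neck, lumbar spine, or total hip when categorizing a participant", applied "for a given DXA test within a given year and compare to the diagnosis of record in the CFFPR". Section 9.3 takes the same measure as the reference for percent agreement and Cohen's kappa, with registry bone data "compared to gold standard clinic DXA scan T-scores". Neither place makes an exception for age at scan.

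Section 2.0 describes an age-dependent convention for the body whose registry is being validated. It says that "the CFF uses Z-scores for children less than 18 years", that the CFF "considers T- and Z-scores as nearly equivalent for persons between ages 18-30 years", and that it "uses T-score findings for persons with CF ages 30 years and older". The same section defines the T-score against a young normal population and the Z-score against an age-matched one.

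The data-collection text is not consistent. Step 12a states: "CF research staff will report T-scores from 3 anatomical sites: femoral neck, lumbar spine and total hip". Table 6 also lists T-scores only; it mentions dates but then specifies the year of the scan. Table 9 in Section 9.1.2 differs: "Results will include T-scores and Z-scores from 3 sites", with the date of the scan. No section says how the Z-scores would be used.

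**The concern.** Participants are adults at enrollment, but the scans are historical. Enrollment starts after pre-testing, expected to end in July 2020, and step 12 reaches back to 2013. Some scans will therefore come from women who were then under 18. For those scans the reference standard is not the score that the protocol says the CFF uses.

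This matters because the analysis asks whether the registry is right. If a minor's registry entry rests on a Z-score and the study category on a T-score, a mismatch may reflect the choice of score and not a registry error. If the scan report carries no T-score, step 12b gives no category at all. And if sites complete the CRF as step 12a reads, the Z-scores needed to sort this out later will not have been collected. Section 3.0 predicts substantial agreement, so an artifact in kappa bears on a stated hypothesis.

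**Working it through.** **The plan's own figure.** The only number attached to this procedure is 100 participants: 10 centers × 10 = 100. It reproduces. No precision or sample size is given for kappa.

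**Inputs.**
- Age at enrollment 18 to under 46 (Table 4).
- Planned mix 383 aged 18–35 and 192 aged 36–45, total 575 (Table 3).
- Scans from 2013 to 2018 (step 12), taken as 2013.0 to 2019.0.
- Enrollment from about 2020.6, after pre-testing (Section 7.0), lasting 12 months (Section 10.4) or 15 months (Section 7.1.1), so to 2021.6 or 2021.85.
- Assumptions: ages uniform within each band, scans uniform over the window.

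**Who was a minor.** Age at scan = age at enrollment − (enrollment date − scan date).
- A woman exactly 18 at enrollment was at youngest 18 − (2021.85 − 2013.0) = 9.15 and at oldest 18 − (2020.6 − 2019.0) = 16.4. All her scans are under-18 scans.
- The enrollment age below which an under-18 scan is possible runs from 18 + (2020.6 − 2013.0) = 25.6 to 18 + (2021.85 − 2013.0) = 26.85.

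**Share affected.** The 18–35 band spans 18 years and holds 383/575 = 0.666 of participants. Mean enrollment date is 2021.1 (12 months) or 2021.225 (15 months). Share = 0.666 × (mean enrollment date − reference date)/18.

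| Quantity | Reference date | 12 months | 15 months |
|---|---|---|---|
| Participants with some of the window under 18 | 2013.0 | 0.666 × 8.1/18 = 30.0% | 0.666 × 8.225/18 = 30.4% |
| Scan time under 18 | 2016.0 (midpoint) | 0.666 × 5.1/18 = 18.9% | 0.666 × 5.225/18 = 19.3% |
| Participants with the whole window under 18 | 2019.0 | 0.666 × 2.1/18 = 7.8% | 0.666 × 2.225/18 = 8.2% |

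With ages flat over 18 to 46, scan time under 18 is 5.1/28 = 18.2% or 5.225/28 = 18.7%.

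**What it could do to kappa (illustration only).** Assume 100 scans, registry categories 20/60/20 (normal/osteopenia/osteoporosis), otherwise perfect agreement, and T-scores that move some under-18 scans one category worse. For 19% of scans under 18 and half of the normal and osteopenia ones shifting:
- Shifts are 0.19 × 0.5 × 20 = 1.9 and 0.19 × 0.5 × 60 = 5.7.
- Observed agreement is (100 − 7.6)/100 = 0.924.
- DXA totals are 18.1, 56.2 and 25.7.
- Chance agreement is (20 × 18.1 + 60 × 56.2 + 20 × 25.7)/10,000 = 0.425.
- Kappa = (0.924 − 0.425)/(1 − 0.425) = 0.87.

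| Scans under 18 | 25% shift | 50% shift | 100% shift |
|---|---|---|---|
| 5% | 99%, kappa 0.98 | 98%, 0.97 | 96%, 0.93 |
| 10% | 98%, 0.97 | 96%, 0.93 | 92%, 0.86 |
| 19% | 96%, 0.93 | 92%, 0.87 | 85%, 0.74 |

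With no shift, agreement stays at 100%. The category mix and the shift fractions are assumed; the documents give neither.

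**The case against.** A reader might infer that correct registry entries will be scored as errors and that agreement must come out too low. The documents do not support that, for four reasons.

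- **The score behind a registry entry is not stated.** Section 2.0 reports a CFF convention, but the registry fields in the Appendix record only a result such as osteopenia or osteoporosis. If an entry was made from a T-score, step 12b matches it.
- **The direction is open.** Suppose the T-score reads lower than the Z-score in a minor. An entry of osteopenia could then become a false disagreement. But an entry of osteopenia that the Z-score would call normal could become a false agreement, and an entry of osteoporosis cannot move lower. Step 10 samples women with a recorded positive diagnosis, so the last two cases are relevant. A scan with no T-score drops out and counts on neither side.
- **The 19% is scan time, not scans, and is not an upper bound.** Women with recorded bone disease may be older than the cohort, and a center a woman attended once in the last two years may not hold her adolescent scans. Both would lower the share. Scans concentrated at younger ages would raise it. Sections 5.0 and 7.3 also describe the draw without the positive-diagnosis restriction.
- **The number of scans is unknown.** The 100 are participants, while step 12b classifies each test.

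It is also fair to say that the T-score rule agrees with the stated CFF convention for scans at 18 and over, about 81% of scan time here. If Table 9 governs the CRF, the scan date and Z-score will be available, and date of birth is held, so an age-specific analysis could still be done.

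These points limit the size and direction of the claim. They do not remove the mismatch: under-18 scans are in scope, the rule treats them like adult scans, and two of the three descriptions of the CRF leave out the Z-score.

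**Conclusion.** The point holds as a defect in the reference standard for under-18 scans. By the protocol's own dates such scans are in scope, and Section 2.0 says the CFF uses a different score for them. They may be misclassified or unclassifiable, and percent agreement and kappa may be distorted by an amount and in a direction that the documents do not fix.

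About 30% of participants and 19% of scan time are exposed, under the Table 3 mix with even ages and even scan timing. The share among the sampled women could be near zero, about that level, or above. In the illustration kappa stays at or above 0.93 when 5% of scans are under 18 and falls to 0.74 in the most extreme case at 19%. These figures show what is possible and are not an estimate of bias.

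The point does not extend to scans at 18 or over under the CFF convention. It concerns a secondary validation objective and leaves the primary exacerbation analysis untouched.

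**What to change.** Reconcile steps 12a and 12b, Table 6, Table 9 and Section 9.3 with Section 2.0 before sites complete the CRFs:

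1. Make step 12a and Table 6 request T-scores, Z-scores and the full scan date, as Table 9 already does. The year alone cannot always show whether a woman was 17 or 18.
2. State in step 12b and Section 9.3 how age at scan enters. One option is to restrict the primary T-score agreement analysis to scans taken at 18 or over. The other is to classify under-18 scans by Z-score, with cutoffs for the three categories written down beforehand; the documents give none now.
3. Report the number of under-18 scans and the number that could not be classified.

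The cost is a CRF alignment and a sentence or two of text. Restriction also loses the under-18 scans: about 19% under the even-spread assumptions, with about 8% of participants having no adult scan time in the window. The true loss may be smaller or larger. The Z-score option keeps those scans but needs the cutoffs agreed first.
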